## 2 DRUG DESCRIPTION

The product of interest is a fixed-dose combination of naltrexone hydrochloride (HCl), 8mg, and bupropion HCl, 90mg, for oral use via extended-release oral tablet. The product is marketed under the trade name CONTRAVE® in the United States (U.S.). It is a combination of an opioid antagonist (naltrexone) and an aminoketone antidepressant (bupropion). Each constituent active ingredient is available separately in various doses and formulations.

Following conventions within previous documents, hereafter we refer to the product CONTRAVE® as the branded product, under regulation. Use of CONTRAVE® or concomitant initiation of its constituent active ingredients, naltrexone and bupropion, will be referred to as NB within this protocol.

CONTRAVE® is indicated as an adjunct to a reduced-calorie diet and increased physical activity for chronic weight management in adults with an initial body mass index (BMI) of:

- 30 kg/m^2 or greater (obese) or
- 27 kg/m^2 or greater (overweight) in the presence of at least one weight-related comorbidity (e.g., hypertension, type 2 diabetes mellitus, or dyslipidemia).

CONTRAVE® is recommended to be initiated according to a dose-escalation schedule beginning with one tablet each morning in week one and increasing to up to two tablets twice daily beginning in week four.

The labeled contraindications include known allergy to any ingredient within CONTRAVE®; uncontrolled hypertension; seizure disorders; anorexia nervosa or bulimia; undergoing abrupt discontinuation of alcohol; use of benzodiazepines, barbiturates, or antiepileptic drugs; chronic opioid use; and taking currently, or within the past 14 days, a monoamine oxidase inhibitor.

As specified in the product labeling under Warnings and Precautions and Limitations of Use, the effect of CONTRAVE® on cardiovascular morbidity and mortality has not been established. Additionally, the safety and effectiveness of CONTRAVE® in combination with other products intended for weight loss, including prescription drugs, over-the-counter drugs, and herbal preparations, have not been established. In this protocol, we propose to evaluate the potential effects of NB on cardiovascular endpoints.

### 3 ABSTRACT

Title:	A Non-Interventional Study to Generate Real-World Evidence on the Cardiovascular Safety of CONTRAVE® in the United States (U.S.)
Background and Rationale:	The fixed-dose combination of naltrexone 8mg and bupropion 90mg extended-release oral tablet is marketed under the trade name CONTRAVE® in the U.S. In this protocol, we propose to generate real-world evidence (RWE) from electronic health records (EHR) and linked claims data to assess the cardiovascular safety of CONTRAVE® and all NB in usual clinical practice.
Research Question and Objectives:	
The main objective of this study is to compare the incidence of the primary endpoint (major adverse cardiovascular events [MACE]) between initiators of NB and initiators of an active comparator, lorcaserin (1.0).
 
The study will also compare the incidence of the secondary endpoint (each component of MACE) between initiators of NB and initiators of lorcaserin, overall and across subgroups of interest (1.1)
 
This study includes three additional objectives to support the assessment of the robustness of the results for the primary and secondary endpoints:
 
 
• To assess the comparability of the results from the same EHR data to the results of the 2018 randomized clinical trial assessing cardiovascular endpoints among lorcaserin users, in a manner consistent with the Randomized Controlled Trials Duplicated Using Prospective Longitudinal Insurance Claims: Applying Techniques of Epidemiology Initiative (RCT DUPLICATE) (2.0);
 
• To quantify differences in cardiovascular safety endpoints between the 2018 trial and the results of this EHR study (2.1);
 
• To conduct other sensitivity analyses, including a self-controlled, case-crossover analysis to quantify the potential effect of NB on MACE (2.2).
 

Study Design:	Retrospective, new-user cohort study.
Population:	The primary study population includes initiators of NB or the active comparator, lorcaserin.

	
Inclusion and exclusion criteria for the main objective will ensure that only new users are included, and that the NB and comparison groups are comparable on risk factors for MACE after application of propensity score (PS) matching weights.
 
Inclusion and exclusion criteria for the additional objectives will align with those used in the 2018 trial assessing cardiovascular endpoints among lorcaserin users, insofar as the data support a comparable replication.
		
Variables:	
The key variables are initiation of NB, initiation of lorcaserin (active comparator), time on treatment, and the endpoint of MACE. The individual components of MACE will also be quantified. Covariates will be derived from clinical measurements, past medical history, diagnoses, observations, and prescription records. Multiple imputation will be applied to address missing data, coupled with PS analyses to address confounding.
		
Data Sources:	
EHR and linked claims data from Arcadia Data Research. The data currently cover approximately 75 million people in the U.S.
		
Study Size:	
There are approximately 37,000 apparent NB initiators in the Arcadia data.
 
There are approximately 16,000 apparent lorcaserin initiators.
		
Data Analysis:	
Descriptive statistics of the study cohorts, multiple imputation of missing covariates, estimation of crude incidence rates of MACE among initiators of NB, and adjusted incidence rates of MACE after applying PS matching weights will be calculated (1.0 and 1.1). Analogs to intention-to-treat and per-protocol cohort analyses will be conducted. The analysis will also follow the principles of the RCT DUPLICATE Initiative (2.0 and 2.1) to assess the concordance between findings in an EHR study to those in the lorcaserin cardiovascular safety endpoints trial. In addition, we will conduct a case-crossover study to assess the effects of NB on MACE (2.2) and other sensitivity analyses.
		
Milestones:	
 
 Start of Data Collection End of Data Collection	September 2014 February 2020	
 
	Start of Data Collection End of Data Collection	September 2014 February 2020
Start of Data Collection End of Data Collection	September 2014 February 2020		

## 4 RATIONALE AND BACKGROUND

The U.S. Food and Drug Administration (FDA) approved CONTRAVE® on September 10, 2014, for chronic weight management in obese adults (body mass index [BMI]  $\geq 30 \text{ kg/m}^2$ ) and in those who are overweight (BMI  $\geq 27 \text{ kg/m}^2$ ) with at least one weight-related comorbidity (e.g., hypertension, type 2 diabetes mellitus, or dyslipidemia). CONTRAVE® is used as an adjunct to a reduced-calorie diet and increased physical activity. The labeling indication includes two Limitations of Use, one of which states that the effect of CONTRAVE® on cardiovascular morbidity and mortality has not been established. Since 2014, real-world data (RWD) on NB have accumulated through use in clinical practice and afford an opportunity to generate RWE on the drug's safety profile. This protocol proposes the generation of RWE from EHRs and linked claims data to assess the cardiovascular safety of NB in usual clinical practice.

We also include several additional objectives; prime among them is assessing the comparability of findings using RWD to those generated from a clinical trial. RWD studies are often more cost-effective and feasible compared to their RCT counterparts. When sufficiently calibrated, RWD studies can reach similar conclusions to RCTs and can contribute meaningfully to evidence generation for therapeutics in real-world clinical practice. The RCT DUPLICATE Initiative supports this goal and was created to quantify differences between RCT findings and corresponding RWD replications, to understand the types of research questions suitable for RWD, and to understand the methods that should be used for such studies. Comparisons to trial results can help to assess and quantify the presence of (potential) biases in RWD studies.

This protocol was developed in accordance with regulatory guidance, draft and international society guidelines, and frameworks for observational database studies involving RWE.

## 5 RESEARCH QUESTIONS AND OBJECTIVES

The study will assess whether patients who initiate treatment with NB are at an elevated risk of MACE compared with patients who initiated treatment with lorcaserin, an active comparator chosen to reduce potential confounding. Lorcaserin was approved in the U.S. under the brand names BELVIQ® and BELVIQ XR® for the same indication as NB, and withdrawn from the market due to cancer safety concerns in 2020. Lorcaserin is not believed to have adverse effects on cardiovascular outcomes. The CAMELLIA-TIMI 61 trial was a comparison of lorcaserin relative to placebo in overweight and obese patients with cardiovascular disease and cardiovascular disease risk factors. The trial found no difference in the rate of cardiovascular events.

The study's main objective is to compare the incidence of the primary endpoint (MACE) between initiators of NB and initiators of lorcaserin (1.0). The study will also compare the incidence of the secondary endpoint, consisting of each *component* of MACE, between initiators of NB and initiators of lorcaserin, across the following subgroups (1.1):

- Patients with obesity (i.e., most recent BMI measurement  $\geq 30$  kg/m^2);
- Patients with a diagnosis of hypertension, regardless of BMI;
- Patients with a diagnosis of type 2 diabetes mellitus, regardless of BMI;
- Patients with a diagnosis of dyslipidemia, regardless of BMI.

The study's additional objectives aimed at testing the robustness of the methods are:

- To assess the comparability of findings from an EHR study to those of a 2018 clinical trial, aligning with the RCT DUPLICATE Initiative (2.0);
- To quantify differences in cardiovascular safety endpoints between the clinical trial and the results of this EHR study (2.1);
- To conduct other sensitivity analyses, including a self-controlled, case-crossover analysis to quantify the potential effect of NB on MACE (2.2).

## 6 RESEARCH METHODS

### 6.1 Study Design

A retrospective cohort study design will be used for the main objective and endpoints. Initiators of NB will be identified between September 2014 and February 2020. Contemporaneously, we will identify all lorcaserin users between 2012 and 2020. A self-controlled, case-crossover design will be used for the sensitivity analysis (2.2).

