### 6.3 Inclusion Criteria

For the main objective (1.0, 1.1), patients are eligible if they meet the following inclusion criteria:

- Have at least one prescription for NB between September 2014 and February 2020, including concurrent prescriptions (within 15 days) for naltrexone and bupropion; or have at least one prescription for lorcaserin;
- Have at least 180 days of data available prior to cohort entry with no evidence of prescriptions or dispensings of NB or lorcaserin;
- Have at least one BMI value available in the 180 days prior to cohort entry, inclusive of the index date;
- Have documentation of at least one outpatient medical visit 180 or more days prior to cohort entry, and at least one healthcare interaction in the 180 days prior to cohort entry;

- Are at least 18 years of age on the cohort entry date.

Of note, having at least one BMI value is the only inclusion criterion that is potentially missing within the EHR. Documentation of at least one outpatient medical visit more than 180 days prior to cohort entry, and at least one healthcare interaction in the 180 days prior to cohort entry is required. This criteria will facilitate the inclusion of individuals who appear to have sufficient engagement with an Arcadia-contributing health system and would have enough clinical data to meet the study objectives.

For the comparability study (2.0 and 2.1), inclusion criteria will be based on the CAMELLIA-TIMI 61 trial, insofar as the information is available in the data. Examples include:

- BMI  $\geq 27 \text{ kg/m}^2$ ;
- Age  $\geq 40$  years with history of documented myocardial infarction (MI) or ischemic stroke  $> 1$  month prior to baseline, peripheral artery disease, revascularization or significant unrevascularized coronary arterial stenosis;
- Women age  $\geq 55$  years or men age  $\geq 50$  years who have type 2 diabetes mellitus without established cardiovascular disease but at least one cardiovascular risk factor (hypertension, dyslipidemia, calculated creatinine clearance  $\geq 30$  to  $\leq 60 \text{ mL/min}$ , or urinary albumin-to-creatinine ratio  $\geq 30 \text{ } \mu\text{g/mg}$ ).

The full list of inclusion criteria are included in the CAMELLIA-TIMI 61 publication and protocol.

Where variables are not available in the EHR or claims data, we will search for suitable proxies based on the literature and the recommendations of a U.S.-licensed physician consultant.

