**Figure 1. NB safety study design**

[figure not shown]

For the cohort, among the subset of patients with EHR data whose records can be linked to health insurance claims, we will assess the concordance between receiving a prescription for NB and lorcaserin (in the EHR) and filling the prescription (in the claims).

The time of entry into the NB cohort will be the date of first prescription for those taking CONTRAVE®, the date of the second overlapping prescription of naltrexone or bupropion in the case of concomitant use of naltrexone and bupropion, or the date of first prescription for lorcaserin from date of approval in the U.S. to withdrawal from the market, as applicable.

In the case-crossover study, a 90-day hazard window will immediately precede the index event date within which the occurrence of a prescription or dispensing will define exposure status. Similarly, a 90-day referent window will precede the hazard window, with exposure status designated comparably. A 30-day washout window between the hazard and referent windows will be used to mitigate any carryover effects from the prior exposure. Please see **Figure 2** for a visual depiction of the case-crossover study design.

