## 9.4 PS Matching Weights

PS matching weights will be used to control for confounding between treatment groups. A logistic regression model will be used to estimate the predicted probability of treatment with NB versus treatment with lorcaserin, conditional on pre-specified covariates. Each patient's PS, or predicted probability from the model, will be the probability that the patient received NB. The complement of each patient's PS (i.e., 1-PS) will be the probability that the patient received lorcaserin. Each patient will be assigned a matching weight, which is a function of their PS and the treatment received. The numerator of the matching weight is the smaller of the PS or the complement of the PS (1-PS). The denominator is the PS if the patient received NB, and it is 1-PS if the patient received lorcaserin. For example, a patient with a PS value of 0.6 (1-PS = 0.4) who received NB would have a matching weight of 0.4/0.6 or 0.667. These weights will be used in regression models to account for confounding.

Similar methods will be used to generate propensity score weights within the CAMELLIA-TIMI 61 comparability cohort. Covariates will include demographics, calendar time of treatment initiation, comorbidities, medications, cardiovascular procedures, and indicators of health care utilization as proxy for overall disease state, care intensity, and surveillance.

Matching weights are the weighting analog of 1:1 PS matching, but include the entire eligible patient population, are more statistically efficient than matching, and produce better balance on covariates. Thus, matching weights standardize the distribution of patient characteristics to the area of common support (or empirical equipoise) in which patients could have reasonably received either treatment.

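### The arms are called contemporaneous, but lorcaserin entry opens in 2012 and NB entry in September 2014, and no form is given for calendar time in the propensity score

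*Combined protocol and SAP*

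**What the plan says.** All references are to the combined protocol and SAP.

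- **6.1 Study Design:** "Initiators of NB will be identified between September 2014 and February 2020". The next sentence reads: "Contemporaneously, we will identify all lorcaserin users between 2012 and 2020".
- **4 Rationale and Background:** the FDA "approved CONTRAVE® on September 10, 2014", so NB entry opens in the month of approval.
- **6.3 Inclusion Criteria:** one bullet dates the NB arm ("Have at least one prescription for NB between September 2014 and February 2020") and leaves the comparator undated ("or have at least one prescription for lorcaserin").
- **6.5.1 Exposure:** comparator entry is "the date of first prescription for lorcaserin from date of approval in the U.S. to withdrawal from the market".
- **3 Abstract, Milestones:** data collection runs from September 2014 to February 2020 and is not split by drug.
- **9.4 PS Matching Weights:** the main PS estimates "the predicted probability of treatment with NB versus treatment with lorcaserin, conditional on pre-specified covariates". A later paragraph opens with "Similar methods will be used to generate propensity score weights within the CAMELLIA-TIMI 61 comparability cohort" and then gives a covariate list that includes calendar time of initiation, with no functional form. The section describes the weights as standardizing to patients who might reasonably have been given either drug.
- **9.5.3:** the weighted Poisson model also adjusts for every PS covariate.

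No section limits lorcaserin entry to the NB window or plans a sensitivity analysis on it. Figure 1 is not shown in the text available and may carry dates.

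**The concern.** A programmer who follows 6.1, 6.3 and 6.5.1 literally would enrol comparators from 2012. Under 6.3, nobody entering before September 2014 can be an NB initiator. That includes users of separate naltrexone and bupropion, which Section 2 says are available individually. Those lorcaserin patients have no NB counterpart, and whether they influence the main estimate depends on a modelling choice that the plan leaves open.

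If calendar time is left out of the PS, 9.5.3 leaves it out of the outcome model too. Changes over time in care, coding or EHR capture would then be mixed with the drug contrast. If it enters as a straight line, a gradual trend is handled but an abrupt or curved change is not. The result is a cardiovascular safety report for FDA (Section 13), so modest shifts in the rate ratio and its interval matter even where power does not.

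**Working it through.** **1. Windows.** September 10, 2014 is 2014.69 and the end of February 2020 is 2020.17. The 2012 start month is not given, so I take openings from 2012.0 to 2013.0. Lorcaserin entry then opens 2014.69 − 2013.0 = 1.69 to 2014.69 − 2012.0 = 2.69 years before NB entry.

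**2. Early share (illustrative).** Inputs from the abstract: about 37,000 NB and about 16,000 lorcaserin initiators. Assumptions: uniform uptake of each drug to 2020.17, and a count of 16,000 that begins when the window opens. The documents date neither.

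- Opening 2012.0: 2.69 / 8.17 = 0.329, or 5,268 patients.
- Opening 2012.5: 2.19 / 7.67 = 0.286, or 4,568 patients.
- Opening 2013.0: 1.69 / 7.17 = 0.236, or 3,771 patients.

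If the count already starts in September 2014, the share is 0.

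**3. Matching weights.** For lorcaserin patients 9.4 gives weight = min(PS, 1−PS) / (1−PS). I fitted a PS on calendar time alone, in four forms. Ranges run over the three openings.

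| Calendar term in PS | Mean weight, early patients | Early share of comparator weight | Weighted gap in mean entry date (years) |
|---|---|---|---|
| None | 1.00 | 24-33% | 0.85-1.35 |
| Linear | 0.67-0.94 | 22-25% | 0.09-0.14 |
| Calendar year | 0.26-0.38 | about 11% | 0.05-0.06 |
| Quarter | 0.06-0.08 | about 3% | under 0.01 |

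A linear term nearly balances the mean entry date yet leaves almost a quarter of comparator weight where there are no NB patients. Year and quarter leave a remainder because the 2014 category straddles September. These are shares of patients. Earlier entrants have longer potential follow-up, so their share of person-time could be larger, but the documents do not allow this to be sized.

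**4. What this could do to a null IRR.** Both inputs below are assumed.

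- *Log-linear trend in MACE, 2-5% a year in either direction.* With no term, the null IRR lies between 0.93 and 1.07. With calendar time linear in both the PS and the outcome model (9.5.3), such a trend is correctly modelled and the null IRR is 1.00.
- *Step of size d in recorded MACE before September 2014.* From the weights alone, IRR = 1 / (1 + share × d). At d = +0.2 and −0.2 with the largest share:
  - none: 1/(1 + 0.329×0.2) = 0.938 and 1/(1 − 0.329×0.2) = 1.070
  - linear (share 0.249): 0.953 and 1.052
  - year (0.112): 0.978 and 1.023
  - quarter (0.028): 0.994 and 1.006

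  Adding a linear term to the outcome model barely helps here (0.953 becomes 0.955). A common window removes the effect.

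**5. Precision cost of restriction.** Section 8.2 states more than 80% power at a relative risk of 2.0, with 2 MACE per 1,000 person-years. Its text gives no follow-up, alpha or comparator size, and Figure 3 is not shown, so that figure cannot be reproduced. Instead I solve for the mean follow-up T that gives 80% power (two-sided 0.05, Wald test on the log rate ratio):

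T = ((1.96 + 0.842) / ln 2)² × (1/(0.004 n₁) + 1/(0.002 n₀))

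| Lorcaserin n₀ | T with n₁ = 37,000 (years) | T with n₁ = n₀ (years) |
|---|---|---|
| 16,000 | 0.62 | 0.77 |
| 12,229 (24% lost) | 0.78 | 1.00 |
| 10,732 (33% lost) | 0.87 | 1.14 |

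Against an all-dates PS with quarter, restriction costs little. Total comparator weight is 11,020 (opening 2012.0) or 12,500 (opening 2013.0), compared with 10,732 or 12,229 patients after restriction.

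**The case against.** The strongest reply is that the plan already deals with this. Section 9.4 names calendar time of initiation, in a section headed for PS weights generally, and its next paragraph returns to matching weights in general. The covariate list in 6.5.3 omits calendar time, but it is introduced as non-exhaustive. It also omits the cardiovascular procedures and utilization measures named in the same 9.4 sentence. Absence from 6.5.3 is therefore weak evidence. A reader might infer that calendar time is left out of the main PS; the documents do not support that. They leave its use in the main PS unclear and its form unstated.

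It is also fair to say that 9.4 does not promise that every enrolled patient could have received either drug. Down-weighting towards common support is the planned mechanism, and with a quarter term it works almost completely. The weighted standardized differences in 9.1 would expose a calendar imbalance if calendar time is among the covariates checked. The September 2014 milestone may mean that a common start was intended and that 6.1 and 6.5.1 are loosely worded.

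What stands after this is that three sections allow or state the wider window, the milestone contradicts it, and the protection depends on an unstated form. A balance check on mean entry date would largely pass under a linear term while the early patients kept most of their weight.

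**Conclusion.** The point holds and should be fixed before analysis. The inconsistency between 6.1, 6.3, 6.5.1 and the milestone is a matter of text and is certain, subject to Figure 1 not being visible. So is the lack of a stated form for calendar time.

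The size is not certain. The 24-33%, 22-25%, 11% and 3% shares rest on uniform uptake and a count opening in 2012-2013, and the true early share may be 0. The IRR shifts rest further on an assumed trend or step. A reader might infer that the main estimate will be materially biased, or biased in a known direction. The documents support neither: they give no trend, no capture history and no early count. The illustrative shifts are at most about 7% and are small against a relative risk of 2.0. With a linear term in both models, the remaining concern is a non-linear or step change, not a steady trend.

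**What to change.** 1. For the main objective (1.0 and 1.1), use one cohort-entry window for both drugs, September 2014 to February 2020, in 6.1, 6.3 and 6.5.1. Reconcile the abstract's milestone with whatever earlier lorcaserin data are kept.
2. Word 6.3 and 6.5.1 to match. For example, 6.3: 'first recorded prescription for lorcaserin falls between September 2014 and February 2020'; 6.5.1: entry is the date of that prescription. Dating only one of the two sections could leave someone prescribed lorcaserin in 2013 and again in 2016 eligible but with no entry date.
3. State in 9.4 that calendar time of initiation, in a flexible form such as quarter, is in the main PS, and show it in the weighted balance table (9.1).
4. Report how many of the approximately 16,000 lorcaserin initiators entered before September 2014, and keep them in a labelled sensitivity analysis. State separately which lorcaserin window objectives 2.0 and 2.1 use.

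**Cost.** Wording changes, plus loss of the early lorcaserin initiators from the main analysis. Their number is not given: it is 0 if the count already starts in September 2014, and about 3,800-5,300 (24-33%) under the stated assumptions. Relative to a PS that already has quarter, only about 3% of comparator weight is lost; relative to a linear term, 22-25%.
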